8.3.1 Appropriateness of efficacy assessments

The microscopy examination methods to quantify the malaria parasite and gametocyte in blood are validated methods ([Sinden et al 2012](#); [White et al 2014](#)).

8.4 Safety

Safety assessments are specified in [Table 8-2](#) with the assessment schedule ([Table 8-1](#)) detailing when each assessment is to be performed.

For details on AE collection and reporting, refer to AE section.

Table 8-2 Assessments & Specifications

| Assessment | Specification |
|----------------------|--|
| Physical examination | 
A complete physical examination will include the examination of general appearance, skin, neck (including thyroid), eyes, ears, nose, throat, lungs, heart, abdomen, back, lymph nodes, extremities, vascular, and neurological. If indicated based on medical history and/or symptoms, rectal, external genitalia, breast, and pelvic exams will be performed.
 
At further visits an abbreviated one will include general appearance. At all visits, patients will be examined for signs of dehydration.
 
At selected visits, head circumference will be measured in cm
 
Information for all physical examinations must be included in the source documentation at the study site. Clinically relevant findings that are present prior to signing informed consent must be recorded as medical history. Significant findings made after signing informed consent which meet the definition of an adverse event must be recorded as an adverse event.
 |
| Vital signs | 
Vital signs will include systolic and diastolic blood pressure, temperature and pulse rate. After the patient has been still for five minutes (as much as possible), systolic and diastolic blood pressure will be measured three times using an automated validated device, e.g. Dynamap/Denshi, with an appropriately sized cuff. Repeat measurements will be made at 1-2 minute intervals and the mean of the three measurements will be used. In case the cuff sizes available are not large enough for the patient's arm circumference, a sphygmomanometer with an appropriately sized cuff may be used.
 
Temperature will be taken using a standard clinical thermometer, for 5 minutes before reading. Clinically notable vital signs are defined in Section 16.1 - Appendix 1.
 |

| Assessment | Specification |
|-------------------|--|
| Height and weight | Height in centimeters (cm) and body weight (in [g] to the nearest 10 g). Whenever available, birth weight (g) will also be collected at baseline visit. Infants should preferably be weighed and measured nude, alternatively wearing clean disposable diapers (weighing infants with too much clothing is one of the most frequent sources of error in infant weight measurements). |

8.4.1 Laboratory evaluations

[figure not shown]
At each site, a local laboratory (validated/accredited) will be used for analysis of all specimens collected, i.e., for hematology and blood chemistry (for either PCR [parasite identification and resistance markers], or PK measurements, a central reference laboratory will be used).

All specimens will be processed and analyzed in the local laboratory. If any results are of clinical concern, a repeat sample will be collected at the next scheduled visit, while remaining within the overall blood volume limit for the patient ([Howie 2011](#)).

| Test Category | Test Name |
|---------------|--|
| Hematology | Hemoglobin, hematocrit, red cell count (RBC and reticulocytes), white blood cell (WBC) count with differential (absolute value preferred, %s are acceptable) (Basophils, Eosinophils, Lymphocytes, Monocytes, Neutrophils, Bands, Other), and platelet count |
| Chemistry | sodium, potassium, magnesium, glucose, creatinine, AST (SGOT), ALT (SGPT), and total bilirubin will be measured |
| Urinalysis | Not applicable |

8.4.2 Other safety evaluations

A specific follow up of liver events will be performed as per [Section 16.2 - Appendix 2](#).

8.4.3 Appropriateness of safety measurements

Safety measurements used in the 43-day follow-up are standard for this indication/subject population and follow WHO guidelines ([WHO 2009; 2018](#))

All safety measurements, [REDACTED] were implemented in the previous study B2306 ([Tiono et al 2015](#); [EMA 2011](#)).

8.5 Additional assessments

No additional tests will be performed on subjects entered into this study.

8.5.1 Clinical Outcome Assessments (COAs)

Not applicable.

8.5.2 Pharmacokinetics

Rationale for Artemether C_{max} (ART C_{max}) as primary endpoint

The previous study B2306 targeting the same population was stopped prematurely because the exposure to artemether and DHA was 2-3 fold higher in the first cohort (>28 days of age and <5 kg body weight) than what had been observed in earlier studies in children ≥ 5 kg body weight. There were no specific safety or efficacy related observations, however, absence of toxicity associated with the higher exposure, especially of neurotoxicity, could not be supported, by historical clinical or non-clinical data nor by the small sample size of study B2306 itself. Therefore, in the present B2307 study, it is hypothesized that if the exposure to artemether and lumefantrine is contained within the range of exposures which have been established to be safe and efficacious in children ≥ 5 kg, a dosing recommendation can be made with reasonable confidence in this vulnerable population. Due to limitations in recruiting the target population, the sample size remains limited and similar to that of Study B2306. Based on available information ([Beckman et al 2013](#)) it is anticipated that a higher artemether exposure remains a major concern of potential neurotoxicity so that monitoring artemether exposure remains critical in this population. Due to the limited number of sampling time points (and limitation of the overall blood volume drawn) in this population, the exposure reference in infants is available only in terms of ART C_{max}, achieving the target maximum concentration (C_{max}) for initial rapid parasitemia reduction (efficacy), ART C_{max} is also an appropriate measure of artemether exposure as artemether PK is described by a one compartment model ; ART C_{max} was therefore selected as the primary endpoint in this study. Nevertheless, other exposure parameters for artemether, DHA and lumefantrine will also be measured, wherever possible, along with safety and efficacy assessments in order to reach a conclusion in this study.

Pharmacokinetic Assessments

Blood samples will be collected for PK at the scheduled time points indicated in one of the 2 possible sample schemes (See [Section 16.3-Appendix 3](#)). When the investigator or their delegate contacts the IRT to confirm that the subject is eligible, the IRT will assign one of the 2 possible sample schemes to the patient (following a 1:1 ratio in each cohort). Due to the limitation in volume and in the number of samples which can be drawn from patients in this study, a total of 5 samples (500 μ L each) will be obtained from each subject. Each subject will be assigned to either of the 2 sampling schemes by the IRT. In every sample, artemether, DHA and lumefantrine will be assessed. The sample points are selected in such a way that will allow

comparison with historical data (concentration at specific time points and ART C_{max}) and also collect useful information about AUC as appropriate.

For artemether, ART C_{max} is determined by collecting samples at 1h and 2h after first dose (as determined in study B2303 and study B2306) and ART C_{max} represents the higher concentration between the concentrations at 1 hour and 2 hours after first dose.

Further details on collection, labeling and shipment of the PK samples can be found in [Section 16.3-Appendix 3](#) and the laboratory manual.

The number of samples/blood draws and total blood volume collected will remain under the limits recommended in this population ([Howie 2011](#)).

9 Study discontinuation and completion

9.1 Discontinuation

9.1.1 Discontinuation of study treatment

Discontinuation of study treatment for a subject occurs when study treatment is stopped earlier than the protocol planned duration and can be initiated by either the subject's parent/legal guardian or the investigator.

The investigator must discontinue study treatment for a given subject if they believe that continuation would negatively impact the subject's well-being.

Study treatment must be discontinued under the following circumstances:

- Subject's parent/legal guardian decision
- Use of prohibited treatment as per recommendations in the prohibited treatment section
- Any situation in which study participation might result in a safety risk to the subject
- Adverse events, abnormal laboratory values, or abnormal test result that indicate a safety risk to the subject (see [Section 16.1-Appendix 1](#)). For liver, see [Section 16.2-Appendix 2](#).
- Unsatisfactory therapeutic effect
- Any laboratory abnormalities that in the judgment of the investigator, taking into consideration the subject's overall status, prevents the subject from continuing participation in the study

Subjects who discontinue study treatment or whose parent/legal guardian decide they do not wish their child to participate in the study further should NOT be considered withdrawn from the study UNLESS they withdraw their consent (see 'Withdrawal of Informed Consent' section).

Where possible, they should return for the assessments indicated in the Assessment Schedule. If they fail to return for these assessments for unknown reasons, every effort (e.g., home visit) should be made to contact the subject's pre-designated contact as specified in the lost to follow-up section. This contact should preferably be done according to the study visit schedule.

If the parent/legal guardian cannot or is unwilling to have the subject attend any visit(s), the site staff should maintain regular contact with them, or with a person pre-designated by them. This contact should preferably be done according to the study visit schedule.

The investigator must also contact the IRT to register the subject's discontinuation from study treatment.

9.1.1.1 Replacement policy

Escalation/de-escalation part

Subjects will not be replaced in the study. However, if the dose is considered as unsuitable in the first few patients of the current cohort, enrollment of another set of new subjects to the current cohort to be treated with a different dose will be considered (for further details, see [Section 3](#) and [Figure 3-2](#)).

Expansion part

During the dose expansion part of each cohort, no replacements will be needed.

9.1.2 Withdrawal of informed consent

Subjects may voluntarily withdraw consent to participate in the study for any reason at any time. Withdrawal of consent occurs only when a subject's legal guardian:

- Does not want the infant to participate in the study anymore, and
- Does not allow further collection of personal data from the infant

In this situation, the investigator should make a reasonable effort (e.g., telephone or any other suitable means) to understand the primary reason for the subject's legal guardian's decision to withdraw his/her consent and record this information.

Study treatment must be discontinued and no further assessments conducted, and the data that would have been collected at subsequent visits will be considered missing.

Further attempts to contact the subject's legal guardian are not allowed unless safety findings require communicating or follow-up.

All efforts should be made to complete the assessments prior to study withdrawal. A final evaluation at the time of the subject's study withdrawal should be made as detailed in [Table 8-1](#).

Novartis will continue to keep and use collected study information (including any data resulting from the analysis of a subject's samples until the time of withdrawal), as provided for in the ICF and according to applicable law.

All biological samples not yet analyzed at the time of withdrawal will no longer be used, as provided for in the ICF, and they will be destroyed according to applicable legal requirements.

9.1.3 Lost to follow-up

For subjects whose status is unclear because they fail to appear for study visits without their legally acceptable representative stating an intention to discontinue or withdraw their child, the investigator must show "due diligence" by documenting in the source documents steps taken to contact the subject's LAR, e.g. dates of home visits, etc. A subject should not be considered as lost to follow-up until due diligence has been completed or until the end of the study.

9.1.4 Early study termination by the sponsor

The study can be terminated by Novartis at any time for any reason. This may include reasons related to the benefit/risk assessment of participating in the study, practical reasons (including slow enrollment), a DMC recommendation or for regulatory or medical reasons. In taking the decision to terminate, Novartis will always consider the subject's welfare and safety. Should early termination be necessary, subjects must be seen as soon as possible and treated as a prematurely withdrawn subject. The investigator may be informed of additional procedures to be followed in order to ensure that adequate consideration is given to the protection of the subject's interests. Specifically, the investigator will inform the subject's legal guardian about the reasons for study termination. The investigator or sponsor depending on the local regulation will be responsible for informing IRBs/IECs of the early termination of the trial.

9.2 Study completion and post-study treatment

All treated subjects will have a safety follow-up visit at Day 43, and at 12 months of age. All SAEs reported during this time period must be reported as described in [Section 10.1.3](#). Documentation of attempts to contact the subject's parent/legal guardian should be recorded in the source documentation.

Study completion is defined as when the last subject finishes their Study Completion visit and any repeat assessments associated with this visit have been documented and followed-up appropriately by the Investigator or, in the event of an early study termination decision, the date of that decision (Each subject will be required to complete the study in its entirety, including the safety follow up at the age of 12 months).

10 Safety monitoring and reporting

10.1 Definition of adverse events and reporting requirements

10.1.1 Adverse events

An adverse event (AE) is any untoward medical occurrence (e.g. any unfavorable and unintended sign [including abnormal laboratory findings], symptom or disease) in a subject or clinical investigation subject after providing written informed consent for participation in the study. Therefore, an AE may or may not be temporally or causally associated with the use of a medicinal (investigational) product.

The investigator has the responsibility for managing the safety of individual subject and identifying adverse events.

Novartis qualified medical personnel will be readily available to advise on trial related medical questions or problems and the relevant contact details will be provided to each site.

The occurrence of adverse events must be sought by non-directive questioning of the subject's parent/legal guardian at each visit during the study. Adverse events also may be detected when they are volunteered by the subject's parent/legal guardian during or between visits or through physical examination findings, laboratory test findings, or other assessments.

Adverse events must be recorded under the signs, symptoms, or diagnosis associated with them, accompanied by the following information (as far as possible) (if the event is serious refer to [Section 10.1.2](#)):

2. The severity grade:
 - mild: usually transient in nature and generally not interfering with normal activities
 - moderate: sufficiently discomforting to interfere with normal activities
 - severe: prevents normal activities
3. Its relationship to the study treatment. If the event is due to lack of efficacy or progression of underlying illness (i.e. progression of the study indication) the assessment of causality will usually be 'Not suspected.' The rationale for this guidance is that the symptoms of a lack of efficacy or progression of underlying illness are not caused by the trial drug, they happen in spite of its administration and/or both lack of efficacy and progression of underlying disease can only be evaluated meaningfully by an analysis of cohorts, not on a single subject
4. its duration (start and end dates) or if the event is ongoing, an outcome of not recovered/not resolved must be reported whether it constitutes a SAE (see [Section 10.1.2](#) for definition of SAE) and which seriousness criteria have been met
5. action taken regarding with study treatment. All adverse events must be treated appropriately. Treatment may include one or more of the following:
 - Dose not changed
 - Dose Reduced/increased
 - Drug interrupted/withdrawn
6. its outcome (i.e. recovery status or whether it was fatal)

Conditions that were already present at the time of informed consent should be recorded in medical history of the subject.

Adverse events (including lab abnormalities that constitute AEs) should be described using a diagnosis whenever possible, rather than individual underlying signs and symptoms.

Adverse event monitoring should be continued until the Day 43 Visit (end of the core follow-up period).

Once an adverse event is detected, it must be followed until its resolution or until it is judged to be permanent (e.g. continuing at the end of the study), and assessment must be made at each visit (or more frequently, if necessary) of any changes in severity, the suspected relationship to the interventions required to treat it, and the outcome.

Information about adverse drug reactions for the investigational drug can be found in the Investigator's Brochure (IB).

Abnormal laboratory values or test results constitute adverse events only if they fulfill at least one of the following criteria:

- they induce clinical signs or symptoms
- they are considered clinically significant
- they require therapy

Clinically significant abnormal laboratory values or test results must be identified through a review of values outside of normal ranges/clinically notable ranges, significant changes from baseline or the previous visit, or values which are considered to be non-typical in subjects with the underlying disease. Alert ranges for laboratory and other test abnormalities are included in [Sections 16.1-Appendix 1](#) and [16.2-Appendix 2](#).

10.1.2 Serious adverse events

An SAE is defined as any adverse event [appearance of (or worsening of any pre-existing)] undesirable sign(s), symptom(s), or medical conditions(s) which meets any one of the following criteria:

- fatal
- life-threatening

Life-threatening in the context of a SAE refers to a reaction in which the subject was at risk of death at the time of the reaction; it does not refer to a reaction that hypothetically might have caused death if it were more severe (please refer to the ICH-E2D Guidelines).

- results in persistent or significant disability/incapacity
- constitutes a congenital anomaly/birth defect
- requires inpatient hospitalization or prolongation of existing hospitalization, unless hospitalization is for:
 - routine treatment or monitoring of the studied indication, not associated with any deterioration in condition
 - elective or pre-planned treatment for a pre-existing condition that is unrelated to the indication under study and has not worsened since the informed consent was signed
 - social reasons and respite care in the absence of any deterioration in the subject's general condition
 - treatment on an emergency outpatient basis for an event not fulfilling any of the definitions of a SAE given above and not resulting in hospital admission
- is medically significant, e.g. defined as an event that jeopardizes the subject or may require medical or surgical intervention to prevent one of the outcomes listed above

Medical and scientific judgment should be exercised in deciding whether other situations should be considered serious reactions, such as important medical events that might not be immediately life threatening or result in death or hospitalization but might jeopardize the subject or might require intervention to prevent one of the other outcomes listed above. Such events should be considered as "medically significant." Examples of such events are intensive treatment in an emergency room or at home for allergic bronchospasm, blood dyscrasias, or convulsions that do not result in hospitalization or development of dependency or abuse (please refer to the ICH-E2D Guidelines).

All malignant neoplasms will be assessed as serious under "medically significant" if other seriousness criteria are not met.

Any suspected transmission via a medicinal product of an infectious agent is also considered a serious adverse reaction.

All reports of intentional misuse and abuse of the product are also considered serious adverse event irrespective if a clinical event has occurred.

10.1.3 SAE reporting

To ensure subject safety, every SAE, regardless of causality, occurring after the subject's parent/legal guardian has provided informed consent and until the last core follow-up study visit must be reported to Novartis safety within 24 hours of learning of its occurrence. Detailed instructions regarding the submission process and requirements are to be found in the investigator folder provided to each site. Information about all SAEs will be collected and recorded on the eCRF Adverse Event Report Form; all applicable sections of the form must be completed in order to provide a clinically thorough report.

All follow-up information for the SAE including information on complications, progression of the initial SAE and recurrent episodes must be reported as follow-up to the original episode within 24 hours of the investigator receiving the follow-up information. An SAE occurring at a different time interval or otherwise considered completely unrelated to a previously reported one must be reported separately as a new event.

If the SAE is not previously documented in the Investigator's Brochure or Package Insert (new occurrence) and is thought to be related to the study treatment, a CMO & PS Department associate may urgently require further information from the investigator for health authority reporting. Novartis may need to issue an Investigator Notification (IN) to inform all investigators involved in any study with the same study treatment that this SAE has been reported.

Suspected Unexpected Serious Adverse Reactions (SUSARs) will be collected and reported to the competent authorities and relevant ethics committees in accordance with EU Guidance 2011/C 172/01 or as per national regulatory requirements in participating countries.

Any SAEs experienced after the last core follow-up study visit should only be reported to Novartis Safety if the investigator suspects a causal relationship to study treatment.

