2.1.1 General definitions

Study treatment: COA566 (artemether: lumefantrine 2.5 mg:30 mg dispersible tablet) is the investigation treatment. As this is a single-arm study there is no control treatment. COA566 is referred to as study treatment in the document.

Treatment group: Treatment group in this study means study drug dose level. Note that although there is only one study treatment, there are 4 possible dose levels (1 to 4 tablets per dose). The treatment group label will always include the study drug level even if there is only one study drug dose level in the whole study. In case that the dose level that passed the exposure check for the first 3 patients in the highest age subgroup in Cohort 2 is not appropriate for either or both the lower age subgroup(s) after the exposure check in 3 patients, the recruitment in these subgroup(s) will be stopped, they will be separated out from Cohort 2 and analyzed separately as needed.

Date of first administration of study treatment: The date of first intake of study treatment within the study.

Date of last administration of study treatment: The date of last intake of study treatment within the study.

Baseline: The last available measurement prior to first administration of study treatment.

Study day: The day of first administration of study treatment is defined as Day 1 (opposed to WHO terminology where this would be Day 0). Day -1 will be the day before Day 1. Day 0 does not exist.

Core period: Core period of the study starting with (and including) Day 1 until (and including) Day 43.

Parasitaemia: *P. falciparum* asexual parasite count greater than zero.

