2.8 Safety analyses

For all safety analyses, the safety set will be used. All listings and tables will be presented by cohort and treatment group.

Safety summaries (tables, figures) include only data from the core period (up to Day 43) with the exception of baseline data which will also be summarized where appropriate (e.g. change from baseline summaries). In particular, summary tables for adverse events (AEs) will include only the core period events, with a start date during that period.

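### After Day 43, SAEs that the investigator does not link to the drug need not reach sponsor safety, and no late SAE enters a summary table; for a neonate this covers about 88% of follow-up time to age one year

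*Protocol*

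**What the plan says.** **Reporting.** Protocol 10.1.3 sets two rules. Every SAE, whatever its cause, "until the last core follow-up study visit must be reported to Novartis safety within 24 hours of learning of its occurrence". After that visit: "Any SAEs experienced after the last core follow-up study visit should only be reported to Novartis Safety if the investigator suspects a causal relationship". Section 9.2, which covers the visits at Day 43 and at 12 months of age, adds no rule of its own. It says "All SAEs reported during this time period must be reported as described in" Section 10.1.3, so the causality condition carries over.

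**Recording.** The same Section 10.1.3 says "Information about all SAEs will be collected and recorded on the eCRF Adverse Event Report Form". That sentence has no time limit and no causality limit. Section 10.1.1 ends the monitoring of adverse events at Day 43.

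**Analysis.** SAP 2.8 says "Safety summaries (tables, figures) include only data from the core period (up to Day 43", with an exception only for baseline data, and it restricts AE tables to events that start in that period. Protocol 12.5.2 says the same. SAP 2.1.1 defines the period: "Core period of the study starting with (and including) Day 1 until (and including) Day 43".

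**The one-year visit.** Protocol Table 8-1 schedules a visit at age 365 days with neurodevelopmental follow-up, head circumference, physical examination and weight/length. None of these depends on a causality judgement.

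**The concern.** The trial exists because artemether exposure in an earlier study of infants under 5 kg was two to three times what was expected. Protocol 8.5.2 states that "higher artemether exposure remains a major concern of potential neurotoxicity". The one-year follow-up is the trial's only long-term look at that risk.

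Protocol 4.1 relies on objective endpoints to limit bias from the open-label design. Which late SAEs reach sponsor safety, however, turns on an investigator's opinion about causality, with no control arm to set it against. Months after a three-day treatment, in a malaria-endemic area, a convulsion or a death is easily attributed to something else. Section 10.1.1 itself says that events due to progression of the underlying illness will usually be classed as not suspected. Convulsions are among the protocol's own examples of medically significant events (10.1.2).

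There is also an oversight consequence. Ad hoc safety reviews can be prompted by SAEs (10.2.1, 12.7). An unsuspected late SAE in a Cohort 1 child need not reach sponsor safety while Cohort 2 is still being dosed.

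**Working it through.** The documents give no figure for the share of follow-up after Day 43, so there is none to reproduce. It follows from the schedule.

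**Inputs**
- Age at first dose, *a*: 1 to 28 days for Cohort 2 (protocol 5.1).
- Elapsed time from Day 1 to Day 43, *c*: 42 days (SAP 2.1.1).
- Age at the end of follow-up, *T*: 365 days (protocol Table 8-1).

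**Formula:** share after Day 43 = (*T* − *a* − *c*) / (*T* − *a*)

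**Base case**
- *a* = 1: 322/364 = 88.5%
- *a* = 15: 308/350 = 88.0%
- *a* = 28: 295/337 = 87.5%

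**Variants for neonates (*a* = 28 to *a* = 1)**
- Core period counted inclusively, *c* = 43: 294/337 to 321/364 = 87.2% to 88.2%
- Day 43 visit at the end of its SAP window (Day 50), *c* = 49: 288/337 to 315/364 = 85.5% to 86.5%
- One-year visit at the early edge of the SAP window, *T* = 335: 265/307 to 292/334 = 86.3% to 87.4%
- One-year visit at the late edge, *T* = 395: 325/367 to 352/394 = 88.6% to 89.3%

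**Cohort 1.** The share falls with age at entry: 294/336 = 87.5% at 29 days and 263/305 = 86.2% at 60 days. At 210 days, an assumed upper age taken from the 1-7 months label in protocol Table 4-2, it is 113/155 = 72.9%.

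**What happens to an SAE under the rules as written**

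| | Starts by Day 43 | After Day 43, suspected | After Day 43, not suspected |
|---|---|---|---|
| Reported to sponsor safety | Yes, within 24 hours | Yes | Not required |
| Recorded on the eCRF | Yes | Yes, on the general sentence in 10.1.3 | Not clear |
| Counted in AE/SAE summaries | Yes, if treatment-emergent | No | No |
| Shown in listings | Yes | If recorded | If recorded |

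**A conflict inside the SAP.** Weight and height are in SAP 2.8.3.2, under the Day 43 limit of SAP 2.8, and are summarised by visit. SAP Table 5-1 nevertheless gives them an analysis window at 335 to 395 days of age. Both cannot hold.

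**The case against.** The strongest reply is that reporting is not collection. The restrictive sentence governs what goes to sponsor safety, while the eCRF sentence in the same section covers all SAEs. The extent of the SAE row in Table 8-1 cannot be read in the text available, so the schedule does not show that SAE recording stops at Day 43. On this reading the plan may already record everything. That is possible, but Section 10.1.3 does not say that unsuspected SAEs after Day 43 are included, and AE monitoring has ended by then. The ambiguity stands.

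The rule is also a defensible choice. The last dose is at 60 hours (2.5 days) and lumefantrine's half-life is about 5 days (protocol 1.1). Day 43 is therefore (42 − 2.5)/5 = about 8 half-lives later, and the protocol describes the 43-day follow-up as standard and in line with WHO guidelines. This supports limiting expedited reporting. It does not explain leaving late SAEs out of the summaries when the stated worry is neurotoxicity and a one-year visit is already planned.

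Section 9.2 does not contradict 10.1.3, since it defers to it.

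Four stronger readings are tempting, and the documents do not support them:
- *That about 88% of the data are causality-filtered.* The figure is a share of calendar time and applies to SAE reports. The one-year assessments most relevant to neurotoxicity are unfiltered. They do cover only children who attend, and they do not count deaths.
- *That no safety table goes beyond Day 43.* The Age-365 window for weight and height points to at least one. The heading of protocol 12.6 is redacted and the available SAP text runs from 2.10 to 2.12, so a one-year neurodevelopmental analysis cannot be ruled out.
- *That a child who dies shows up only as a missed visit.* Disposition is tabulated for the follow-up epoch (SAP 2.3.1), AE listings are not cut at Day 43 (SAP 2.8.1), and loss to follow-up requires documented tracing (protocol 9.1.3).
- *That a number of missed deaths can be given.* The documents contain no mortality rate for this period.

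**Conclusion.** The point holds in a limited form. From Day 43 to 12 months of age, unsuspected SAEs, including deaths and convulsions, need not be reported to sponsor safety. No late SAE, suspected or not, enters a planned AE or SAE summary. Whether the unsuspected ones reach the eCRF is unclear.

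The filter covers about 88% of a neonate's follow-up time (85.5% to 89.3% across the visit windows), and less for older Cohort 1 infants. This assumes that the child is followed to the one-year visit and that Section 10.1.3 is applied as written. The number of events affected cannot be calculated, because the documents give neither a late SAE rate nor the share likely to be judged unrelated. The direction is clear: the filter can only lower the count of late SAEs reported to sponsor safety. The primary PK analysis and the sample size are untouched. This is a worthwhile, inexpensive improvement.

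**What to change.** 1. **Protocol 9.2 and 10.1.3:** state that all deaths and SAEs from Day 43 to 12 months of age are recorded on the eCRF, regardless of causality, at the existing one-year visit or contact. Name convulsions and neurological or developmental diagnoses explicitly. Expedited reporting can stay limited to suspected events.
2. **SAP 2.8 (and protocol 12.5.2):** add one table, by cohort and dose level, of deaths and SAEs starting after Day 43, with each child's 12-month status (seen, died, lost).
3. **SAP 2.8 and Table 5-1:** reconcile the Day 43 limit with the Age-365 window for weight and height, and state which one-year assessments will be tabulated.

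**Cost:** a short amendment, a few eCRF fields at a visit that already takes place, and one table. For a neonate, caregivers would have to recall events over 295 to 322 days, or about 10 months, so minor detail will be less reliable than deaths and admissions. Children already past 12 months would need retrieval from source records.
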